8. RESEARCH QUESTION AND OBJECTIVES

What are incidence rates of safety events of special interest in patients with RA who initiate treatment with Ruxience and are enrolled in the BSRBR-RA?

9. RESEARCH METHODS

To estimate incidence rates of infection, including serious infections, malignancies, cardiovascular (CV) events and events associated with use during pregnancy among all patients with RA in the BSRBR-RA who initiate treatment with Ruxience.

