9.2.1. Inclusion Criteria

1. Eligible for inclusion in BSRBR-RA;
2. Newly initiated treatment with Ruxience for RA;
3. Age >16 years at the initiation of Ruxience treatment.

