9.2.2. Exclusion Criteria

There are no exclusion criteria for this study.

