9.3.2. Endpoints

The BSRBR-RA is an existing, efficient data collection system for evaluating a range of safety outcomes associated with therapies used to treat RA including cancers,^{11,18} cardiovascular events¹⁹ and serious infections.¹⁷ The endpoints collected in BSRBR-RA are events associated with RA itself and therapies used to treat moderate to severe disease. The following events of interest have been pre specified for this study.

1. Hospitalised infections overall.
2. NMSC.
3. Cardiac disorders: including but not limited to heart failure, coronary artery disease, myocardial infarction, and other cardiac disorders.
4. Malignancies, excluding NMSC.
5. Events associated with use during pregnancy.

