9.5. Study Size

This is a descriptive study without pre-specified hypotheses, therefore there is no minimum sample size requirement. All Ruxience-treated patients with data in the BSRBR-RA during the study period will be included in this study. Table 1 displays precision estimates for reported incidence proportions of safety events in Ruxience RMP.

Table 1. Precision Estimates for Reported Incidence Proportions of Safety Events in Ruxience RMP²

Condition	Incident Count	Population at Risk	Incidence Proportion	Lower Bound of 95% CI	Upper Bound of 95% CI
Any infection (including serious infection)	22	73	0.301	0.199	0.420
Serious infection	3	73	0.041	0.009	0.115
Malignancy (excluding NMSC)	1	73	0.014	0.000	0.074
NMSC	0	73	0.000	0.000	0.049
CV events	3	73	0.041	0.009	0.115
Events during pregnancy	0	73	0.000	0.000	0.049

NMSC, non-melanoma skin cancer; CV, cardiovascular; CI, confidence interval.

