9.7. Data Analysis

All statistical analyses will be performed by BSRBR using Stata. The annual analyses will include all patients who have received Ruxience (baseline characteristics) and event incidence reports will include all patients with study follow-up data.

Analyses will be undertaken at 12 monthly intervals and will include recruitment details, baseline characteristics and crude event rates.

The final analysis will provide the incidence rates of safety events of interest overall. If sample size allows, additional analysis in subgroups by gender and new users versus switcher from originator will be undertaken.

The general analytic approach will be descriptive and include rates of events of interest among Ruxience-treated patients. Data will be presented as number of events, incidence rates and 95 % confidence intervals. Such analyses will be performed by and at the direction of BSRBR based on an a priori statistical analysis plan (SAP) maintained by University of Manchester and shared with the Sponsor. The codes will be harmonised with other registers conducting similar analysis. A draft set of MedDRA codes is included in:

Index Date

The Index Date is the date of Ruxience initiation. Patients who switch from another therapy to Ruxience while they are enrolled in BSRBR-RA are eligible for enrollment, and the index date will be the date of Ruxience initiation.

Risk Window

Patients will be evaluated for safety events of interest while exposed to Ruxience and accrue person-time from Index Date until the first occurrence of the event of interest, death, date of last scheduled clinical data provision to the register, lost to follow up, exit from the register or completion of 3 years of follow up. The final report will censor all patients at 3 years after Date of Study Start. Follow up will be uniquely determined for each safety endpoint of interest.

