Some outcomes of interest in this study are thought to potentially occur at a higher rate while on the drug, but that increased risk subsides after the drug is discontinued (ie, serious infections, CV events). In these situations, these events will be calculated using a risk window from Ruxience initiation until 270 days (eg, 9 months) after last infusion based on Ruxience's half-life and mechanism of action. This does not apply to patients who were lost to follow-up, have exited the registry, completed 3 years of follow-up or for whom the most recent date of clinical data provision to the register is within the 270 day window, in which case data will be censored on that date instead. Based on The National Institute for Care and Health Excellence (NICE) guidelines on the use of rituximab treatment, most patients will not be considered for further treatment with Ruxience until at least 6 months from the date of last infusion.

For non-melanoma skin cancer (NMSC) and other malignancies, the manifestation of which is expected to be delayed relative to the time of exposure, the outcomes will be evaluated from drug initiation until the first event, loss to follow up or completion of 3 years of follow up, reflecting a once exposed always at risk paradigm.

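### The pregnancy incidence rate is set over all Ruxience initiators, men and women past childbearing age included, and no end of exposure is defined for this endpoint

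*Protocol*

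**What the plan says.** The objective, printed under Protocol section 9 (Research Methods), is to estimate incidence rates of several event groups, the last being "events associated with use during pregnancy among all patients with RA in the BSRBR-RA who initiate treatment with Ruxience". Section 9.3.2 lists the endpoint as "Events associated with use during pregnancy", with no unit, event definition or at-risk group. Table 2 in Annex 1, which defines select safety endpoints, has no pregnancy row.

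The only demographic limit on entry is "Age >16 years at the initiation of Ruxience treatment" (section 9.2.1), and section 9.2.2 adds: "There are no exclusion criteria for this study".

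Table 1 in section 9.5 carries the row "Events during pregnancy 0 73 0.000 0.000 0.049". In order, the figures are incident count, population at risk, proportion and 95% limits.

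On person-time, the Risk Window text in section 9.7 begins: "Patients will be evaluated for safety events of interest while exposed to Ruxience and accrue person-time from Index Date until the first occurrence". The other stops are death, last scheduled data provision, loss to follow-up, exit from the register and 3 years of follow-up. The text then sets two special windows. One ends 270 days after the last infusion, for outcomes whose "increased risk subsides after the drug is discontinued (ie, serious infections, CV events"). The other, for NMSC and other malignancies, treats a patient as at risk indefinitely once exposed. Pregnancy is named in neither.

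**The concern.** An incidence rate is interpretable only if the people in the denominator can have the event. Here men and women past childbearing age would add person-time but can never add a pregnancy event. The result would then move with the age and sex mix of the patients who receive Ruxience, whatever happens in exposed pregnancies.

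Section 7 says pregnancy is included because the risk management plan classes it as missing information. A near-zero rate spread over mostly non-susceptible person-time could be read as reassurance while saying almost nothing about that gap.

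The exposure window matters for the same reason. An endpoint about use during pregnancy needs a rule for when a pregnancy counts as exposed. The protocol supplies a rule for infections, cardiovascular events and malignancies, but not for this endpoint.

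**Working it through.** **1. Reproduce Table 1.** The inputs are the counts and the 73 patients in section 9.5. For 0 events in n patients, the exact (Clopper-Pearson) two-sided 95% upper limit is 1 − 0.025^(1/n). With n = 73 this is 0.049, as printed. The other five rows also reproduce to three decimals by the same method. The arithmetic in the table is sound; the question is whether 73 is the right n for pregnancy.

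**2. Dilution of the rate.** Let E be the number of pregnancy events, T the total person-time, and f the share of T from women who could become pregnant.
- Rate over all patients: E / T.
- Rate over women who could become pregnant: E / (f × T).
- Ratio of the second to the first: 1/f.

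The documents give no age or sex mix, so f is an assumption. I use 5% to 30%. For scale, assume 73 patients followed for 3 years each (73 × 3 = 219 person-years) and 1 event. The all-patient rate is then 1000/219 = 4.6 per 1,000 person-years.

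| Assumed f | Dilution 1/f | Rate per 1,000 person-years, eligible women only | n = 73 × f, rounded | Upper 95% limit for 0/n |
|---|---|---|---|---|
| 5% | 20 | 91.3 | 4 | 0.602 |
| 10% | 10 | 45.7 | 7 | 0.410 |
| 20% | 5 | 22.8 | 15 | 0.218 |
| 30% | 3.3 | 15.2 | 22 | 0.154 |

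The last column compares with the 0.049 in Table 1. It shows how far the printed limit depends on counting all 73 as at risk.

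**3. The window.** Setting the parts of section 9.7 side by side:
- Opening sentence: evaluation is while exposed, but the end of exposure is not defined.
- General stops: neither discontinuation nor time since last infusion is listed, and the latest stop is 3 years.
- 270-day window: tied to serious infections and cardiovascular events.
- Ever-exposed window: tied to NMSC and other malignancies.

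To see how much depends on the choice, take a patient with a single infusion at the index date and a full 3 years of follow-up. Then 270 / (3 × 365.25) = 0.246, so about 75% of the follow-up lies more than 270 days after the infusion. This is an extreme case. Repeat infusions shorten that share, and so does the rule that the final report censors everyone at 3 years after study start.

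**The case against.** The strongest reply is that the phrase about all patients names the source cohort for a combined list of event groups. The title page and Abstract word the objective without the word all, and no sentence says outright that men contribute person-time to the pregnancy rate. Section 9.7 also says follow-up is determined separately for each endpoint and refers to a statistical analysis plan that is not shown. Part of this stands: that plan could set a narrower denominator. But the protocol does not simply leave the matter open. It fixes the population in the objective, and nowhere does it mention women of childbearing age or exposed pregnancies. The endpoint-specific sentence concerns follow-up, not who is at risk, and the rules after it omit pregnancy.

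Table 1 can fairly be called weak evidence of intent. It shows proportions taken from the risk management plan, not rates planned for this study, and the age and sex mix of those 73 patients is unknown. Even so, its "Events during pregnancy" row labels all 73 as the population at risk.

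Section 9.7 also softens the harm. Event counts are reported beside rates, so a zero would be visible, and a gender subgroup is planned if numbers allow. That subgroup is conditional, would not remove older women, and would not give a result per exposed pregnancy.

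On the window, a reader might infer that a pregnancy conceived years after a single course would plainly count as exposed. The text does not support that: it says while exposed, and the endpoint itself is worded as use during pregnancy. What stands is the gap, since no end of exposure is defined and the listed stops point the other way.

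**Conclusion.** The point holds in two parts.

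First, the objective and Table 1 set a denominator for pregnancy events that includes people who cannot become pregnant. The direction is certain for any cohort containing men or women past childbearing age: the rate is too low by 1/f. The size is not known. A reader might take one of the factors in the table as the expected dilution, but the documents contain nothing from which to estimate f. The 20- to 3.3-fold range for f of 5% to 30%, and the upper limits of 0.602 to 0.154 in place of 0.049, are illustrations only.

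Second, the exposure window for pregnancy is undefined, because the opening words and the list of stops in section 9.7 conflict and neither special window covers this endpoint. This is an ambiguity to resolve, not a stated rule that patients remain exposed indefinitely.

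The study is descriptive and no decision rule turns on this rate, so the rest of the analysis is unaffected. It should still be corrected, because as written the rate cannot inform the missing-information item for which it is collected.

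**What to change.** For pregnancy events:

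- Limit the rate's denominator to person-time of women of childbearing age, with the age limits stated. Section 9.3.1 already lists age and gender as baseline data.
- Always report the number of exposed pregnancies beside the rate.
- Assign the endpoint an explicit exposure window in section 9.7 that reconciles the while-exposed wording with the list of stops and the two special windows.
- Where the register holds the data, also report time from last infusion to conception, and pregnancy outcomes as counts and proportions of exposed pregnancies with exact confidence intervals. The protocol does not say that conception dates or outcomes are captured, so this needs checking with the register first.
- Delete the Table 1 pregnancy row, or restate it on the women of childbearing age among the 73 if that number is known.

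The cost is a wording change to the objective, and so a protocol amendment as well as analysis-plan text. The denominator will be small and the interval wide. The first three items need only age, gender, treatment dates and the pregnancy reports themselves; the fourth may need further data.

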9.1. Study Design

This is an active surveillance study using existing data within the BSRBR-RA, an ongoing, prospective, observational cohort study started in 2001 with the primary aim of studying the safety of new therapies for RA during routine post-marketed clinical use.

9.2. Setting

The BSRBR-RA was established in 2001 to study the safety of biologic therapies in RA patients living in the UK. For the first 7-8 years the main focus was on the study of the safety profile of the first three tumor necrosis factor inhibitor (TNFi) agents (ie, adalimumab (ADA), etanercept (ETA) and infliximab (INF) as a class and as individual therapies. At the time the register was established, the most appropriate comparison group for these three TNFi agents was patients with active RA receiving treatment with csDMARDs. The register remains a relevant resource for studying the safety profile of new biologic, biosimilar and other targeted therapies as they receive National Institute for Health and Clinical Excellence (NICE) approval and are used in real world practice where patients have more diverse clinical background and comorbidities than a typical clinical trial population.

Unique features of BSRBR-RA include recruitment and collection of data from parallel comparison groups of patients consisting of (i) those with active RA who were treated with csDMARDs, and (ii) those with active RA who are biologic naïve treated with TNFi, a high proportion of recruited patients in the UK (>80%), and linkage with national mortality and malignancy registries.¹⁶ Several studies have been conducted using data from the BSRBR-RA including work regarding risks of infections,¹⁷ and malignancies.^{18,11} All patients within the BSRBR-RA provided informed and signed consent for participation (Study Reference 00/8/053).

External validity, ie, generalisability to RA patients who are not enrolled in the register, is maximised by encouraging physicians to enrol each and every patient meeting inclusion criteria, regardless of their baseline demographic or clinical characteristics or treatment history.

9.2.1. Inclusion Criteria

1. Eligible for inclusion in BSRBR-RA;
2. Newly initiated treatment with Ruxience for RA;
3. Age >16 years at the initiation of Ruxience treatment.

9.2.2. Exclusion Criteria

There are no exclusion criteria for this study.

9.3. Variables

This study will focus on specific variables routinely captured in the BSRBR-RA and include baseline patient characteristics (ie, clinical and demographic characteristics, comorbidities and current and past therapies), and safety events of special interest including serious infections, malignancies, CV events, and events associated with use during pregnancy.

9.3.1. Baseline Data

Baseline data are derived from BSRBR-RA reported by the recruiting clinician (or patient where noted), using a standardised form:

1. Diagnosis (including the presence or absence of those features listed in 1987 American College of Rheumatology (ACR) criteria for RA);
2. Age at treatment start, gender, year of recalled symptom onset, year of diagnosis;
3. Ethnicity (patient form);
4. Previous drug history of immunosuppressive csDMARDs and biologics, biosimilar or other new advanced therapy, including duration of therapy recorded as start month/year;
5. Comorbidity (ie, [http://bsrbr.org/hospitals/data collection/](http://bsrbr.org/hospitals/data%20collection/));
6. All current therapy for all illnesses.

9.3.2. Endpoints

The BSRBR-RA is an existing, efficient data collection system for evaluating a range of safety outcomes associated with therapies used to treat RA including cancers,^{11,18} cardiovascular events¹⁹ and serious infections.¹⁷ The endpoints collected in BSRBR-RA are events associated with RA itself and therapies used to treat moderate to severe disease. The following events of interest have been pre specified for this study.

1. Hospitalised infections overall.
2. NMSC.
3. Cardiac disorders: including but not limited to heart failure, coronary artery disease, myocardial infarction, and other cardiac disorders.
4. Malignancies, excluding NMSC.
5. Events associated with use during pregnancy.

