ANNEX 1. LIST OF STAND ALONE DOCUMENTS

Table 2. ICD and MedDRA Codes for Select Safety Endpoints

Event	ARTIS		BIOBADASER, BSRBR, RABBIT
	Operationalisation	Validation ICD	Operationalisation (Final list TBD based on reported endpoints)
Serious infections	Hospitalisations in the Patient Register listing as main diagnosis ICD10-codes below. If main diagnosis is RA, contributory diagnoses are also considered. A00-B99 (excluding A33 and A50), D73.3, E32.1, G00-G02, G04.2, G05-G07, H00.0, H44.0, H60.0-H60.3, H66-H67, H70, I30.1, I40.0, J00-J22, J32, J34.0, J36, J39.0-J39.1, J44.0, J85, J86, K04.4, K04.6, K04.7, K10.2, K11.3, K12.2, K14.0, K57.0, K57.2, K57.4, K57.8, K61, K63.0, K65.0, K65.1, K65.2, K65.9, L00-L08, L30.3, M00-M01, M46.2-M46.5, M60.0, M65.0, M71.0, M71.1, M72.6, M86, N13.6, N15.1, N15.9, N30.0 N30.8, N34.0, N41.2, N43.1, N45.2, N45.3, N45.4, N48.2, N61, N70, N73, N75.1.	This algorithm has not been specifically validated in ARTIS, but the register itself is subject to strict quality assurance routines and has been validated several times. References: Ludvigsson et al. External Review and Validation of the Swedish National Inpatient Register, BMC Public Health, 2011 (11):450. http://www.socialstyrelsen.se/register/halsodataregister/patientregistret/inenglish .	Hospitalisation and/or use of parenteral antibiotics + MedDRA Infections and Infestations SOC 10021881.

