CV risk	Major Acute Cardiovascular Events (MACE), combines MI, stroke, and fatal cardiovascular events: I00-I99 as main cause of death, or I20.0, I21, I60-I64 as diagnosis in in- or outpatient care.	See Serious Infections ‘Outcome’ was defined as any first-ever acute coronary syndrome (ACS) event, which in turn was defined as a primary discharge diagnosis of acute myocardial infarction or unstable angina pectoris, or as acute myocardial infarction being the underlying cause of death. For discharge diagnoses, the date of admission to hospital was considered the event date. This outcome definition has	Fatal and non-fatal 10000891 Acute myocardial infarction; 10006147 Brain stem infarction; 10006148 Brain stem ischaemia; 10008034 Cerebellar infarction; 10008088 Cerebral artery embolism; 10008120 Cerebral ischaemia; 10008190 Cerebrovascular accident; 10014498 Embolic stroke; 10019005 Haemorrhagic cerebral infarction; 10019016 Haemorrhagic stroke; 10024033 Lateral medullary syndrome; 10028596 Myocardial infarction; 10028602 Myocardial necrosis; 10033697 Papillary muscle infarction; 10043647 Thrombotic stroke; 10049768 Silent myocardial infarction; 10051078 Lacunar infarction; 10055677 Haemorrhagic

090177e1953dcb50Approved\Approved On: 16-Oct-2020 13:28 (GMT)

Table 2. ICD and MedDRA Codes for Select Safety Endpoints

Event	ARTIS		BIOBADASER, BSRBR, RABBIT
	Operationalisation	Validation ICD	Operationalisation (Final list TBD based on reported endpoints)

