		
previously been validated in a Swedish early RA cohort, with a positive predictive value of 95%. In addition, a regional validation study of hospitalised acute MI and stroke found positive predictive values of 96% and 94% respectively, in the period 1977 to 1987.
 
References: https://onlinelibrary.wiley.com/doi/epdf/10.1002/art.39267 Mantel et al. Risk Factors for the Rapid Increase in Risk of Acute Coronary Events in Patients With New-Onset Rheumatoid Arthritis. A Nested Case-Control Study. Arthritis & Rheumatology. 2015; 67(11):2845-2854.
 
Lindblad et al. Validity of register data on acute myocardial infarction and acute stroke. Scandinavian Journal of Public health 1993; 21 (1):3-9.
	
transformation stroke; 10056237 Migrainous infarction; 10059613 Stroke in evolution; 10060839 Embolic cerebral infarction; 10060840 Ischaemic cerebral infarction; 10061256 Ischaemic stroke; 10062573 Brain stem thrombosis; 10064961 Thalamic infarction; 10066591 Post procedural stroke; 10066592 Post procedural myocardial infarction; 10067167 Cerebellar embolism; 10067347 Thrombotic cerebral infarction; 10067462 Millard-Gubler syndrome; 10068621 Cerebellar ischaemia; 10068644 Brain stem stroke; 10069020 Basal ganglia infarction; 10070671 Cerebral septic infarct; 10070754 Inner ear infarction; 10071043 Basal ganglia stroke; 10071260 Carotid angioplasty; 10073945 Perinatal stroke; 10074422 Brain stem embolism.
 
Fatal only
 
10002886 Aortic aneurysm rupture; 10003173 Arterial rupture; 10003210 Arteriosclerosis; 10003212 Arteriosclerosis moenckeberg-type; 10006145 Brain stem haemorrhage; 10007522 Cardiac asthma; 10007554 Cardiac failure; 10007556 Cardiac failure acute; 10007558 Cardiac failure chronic; 10007559 Cardiac failure congestive; 10007559 Cardiac failure congestive; 10007560 Cardiac failure high output; 10007625 Cardiogenic shock; 10007684 Carotid arterial embolus; 10007686 Carotid artery aneurysm; 10007688 Carotid artery thrombosis; 10008023 Cerebellar artery thrombosis; 10008030 Cerebellar haemorrhage; 10008076 Cerebral aneurysm ruptured syphilitic; 10008086 Cerebral arteriovenous malformation haemorrhagic;

090177e1953dcb50\Approved\Approved On: 16-Oct-2020 13:28 (GMT)

Table 2. ICD and MedDRA Codes for Select Safety Endpoints

Event	ARTIS		BIOBADASER, BSRBR, RABBIT
	Operationalisation	Validation ICD	Operationalisation (Final list TBD based on reported endpoints)

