			10008089 Cerebral artery occlusion; 10008092 Cerebral artery thrombosis; 10008111 Cerebral haemorrhage; 10008118 Cerebral infarction; 10008132 Cerebral thrombosis; 10018985 Haemorrhage intracranial; 10022758 Intracranial aneurysm; 10022840 Intraventricular haemorrhage; 10022841 Intraventricular haemorrhage neonatal; 10024119 Left ventricular failure; 10024242 Leriche syndrome; 10034476 Pericardial haemorrhage; 10036511 Precerebral artery occlusion; 10039163 Right ventricular failure; 10039330 Ruptured cerebral aneurysm; 10042316 Subarachnoid haemorrhage; 10042434 Sudden death; 10047279 Ventricle rupture; 10048380 Aneurysm ruptured; 10048761 Atrial rupture; 10049418 Sudden cardiac death; 10049993 Cardiac death; 10050403 Carotid artery dissection; 10051093 Cardiopulmonary failure; 10051328 Carotid aneurysm rupture; 10052019 Femoral artery occlusion; 10053633 Cerebellar artery occlusion; 10053649 Vascular rupture; 10053949 Vascular pseudoaneurysm ruptured; 10055803 Haemorrhage coronary artery; 10058178 Aortic occlusion; 10060874 Aortic rupture; 10060953 Ventricular failure; 10060964 Arterial haemorrhage; 10062585 Peripheral arterial occlusive disease; 10062599 Arterial occlusive disease; 10063081 Acute left ventricular failure; 10063082 Acute right ventricular failure ; 10063083 Chronic left ventricular failure; 10063084 Chronic right ventricular failure; 10064595 Haemorrhagic arteriovenous malformation; 10064601 Iliac artery occlusion; 10065441 Venous haemorrhage; 10065558 Aortic

090177e1953dcb50\Approved\Approved On: 16-Oct-2020 13:28 (GMT)

Table 2. ICD and MedDRA Codes for Select Safety Endpoints

Event	ARTIS		BIOBADASER, BSRBR, RABBIT
	Operationalisation	Validation ICD	Operationalisation (Final list TBD based on reported endpoints)
			arteriosclerosis; 10067057 Basal ganglia haemorrhage; 10067116 Carotid arteriosclerosis; 10068119 Aortic dissection rupture; 10068119 Aortic dissection rupture; 10068230 Cardiorenal syndrome; 10069694 Brachiocephalic artery occlusion; 10069695 Subclavian artery occlusion; 10069696 Coeliac artery occlusion; 10071716 Vertebral artery dissection; 10072043 Central nervous system haemorrhage; 10072789 Iliac artery rupture; 10073565 Intracranial artery dissection; 10073565 Intracranial artery dissection; 10073681 Epidural haemorrhage; 10075449 Brachiocephalic arteriosclerosis; 10076203 Radiation associated cardiac failure.

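### Section 9.3.2 defines the CV endpoint as cardiac disorders, Table 2 as a MACE-type list, and Table 2 leaves out some non-fatal stroke terms

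*Protocol*

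**What the plan says.** Section 9.3.2 lists the events pre-specified for the study. Item 3 is "Cardiac disorders: including but not limited to heart failure, coronary artery disease, myocardial infarction, and other cardiac disorders". It is open-ended within cardiac disorders and does not name stroke.

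The objectives (Abstract, and the opening of Section 9) and Table 1 speak only of cardiovascular or CV events, without a definition.

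Table 2 in Annex 1 has a CV risk row. Its ARTIS column reads "Major Acute Cardiovascular Events (MACE), combines MI, stroke, and fatal cardiovascular events" and takes stroke from the diagnosis codes, with no fatality condition: "I20.0, I21, I60-I64 as diagnosis in in- or outpatient care". Its column for BIOBADASER, BSRBR and RABBIT has two blocks:

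- The first opens "Fatal and non-fatal 10000891 Acute myocardial infarction" and holds MI and stroke terms, among them "10060840 Ischaemic cerebral infarction; 10061256 Ischaemic stroke".
- The second counts only fatal events. It holds the heart-failure terms, beginning "10007554 Cardiac failure; 10007556 Cardiac failure acute; 10007558 Cardiac failure chronic", and also "10008118 Cerebral infarction; 10008132 Cerebral thrombosis".

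The header of that column is "Operationalisation (Final list TBD based on reported endpoints". Section 9.7 calls the codes a draft, and says that the analyses follow an a priori SAP and that codes will be harmonised with other registers. Item 6.2 of the ENCePP checklist points to Appendix 1, evidently Annex 1, for how outcomes are defined and measured.

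**The concern.** Impact on cardiovascular disease is one of the four RMP topics that the study is meant to address. Its only product on that topic is an incidence rate, and no comparator is planned against which an error of definition might cancel. If two sections define the numerator differently, two analysts working correctly from the same Protocol would report different endpoints under one name. If, in addition, the list that will probably be programmed drops some surviving stroke patients because of the term chosen at coding, the rate is too low for what the row says it measures.

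**Working it through.** **1. The two definitions side by side, for a patient who survives the event**

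| Event | Section 9.3.2, item 3 | Table 2, BSRBR column |
|---|---|---|
| Myocardial infarction | counts | counts |
| Heart failure | counts (named) | not counted; all cardiac-failure terms are fatal-only |
| Coronary artery disease without infarction | counts (named) | no general term in the non-fatal block |
| Ischaemic stroke | not named, and not a cardiac disorder | counts |

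Heart failure is in the first set and not the second; ischaemic stroke is in the second and not the first. Neither set contains the other, so neither rate bounds the other.

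**2. Stroke terms within Table 2**

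- Counted when non-fatal: Cerebrovascular accident, Cerebral ischaemia, Ischaemic stroke, Haemorrhagic stroke, Lacunar infarction, and the Ischaemic, Thrombotic and Embolic forms of cerebral infarction.
- Counted only if fatal: Cerebral infarction, Cerebral thrombosis, Cerebral haemorrhage, Subarachnoid haemorrhage, and other intracranial bleeding terms such as Haemorrhage intracranial.

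A survivor coded Haemorrhagic stroke counts; a survivor coded Cerebral haemorrhage does not. A survivor coded Ischaemic cerebral infarction counts; one coded with the plain parent term does not. The ARTIS column of the same row applies no such split to stroke. The non-fatal block also contains Carotid angioplasty, which is a procedure rather than an event.

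**3. The only CV figure in the Protocol**

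Table 1 gives 3 events in 73 patients, 0.041 (95% CI 0.009 to 0.115).

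- Point estimate: 3/73 = 0.0411.
- Exact (Clopper-Pearson) limits: lower = 2.5% quantile of Beta(3, 71) = 0.0086; upper = 97.5% quantile of Beta(4, 70) = 0.1154.

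The row reproduces. Table 1 does not say which definition produced the 3 events, so it cannot settle the conflict.

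**4. What a change of definition can do at such counts (illustration only)**

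Reclassifying one event changes a count of 3 by 1/3 = 33%:

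- 2/73 = 0.027 (0.003 to 0.095)
- 4/73 = 0.055 (0.015 to 0.134)

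Suppose a share s of CV events is non-fatal but coded to fatal-only terms. The Protocol gives no s, so the values here are assumed. The counted proportion is 0.0411 × (1 − s): 0.039 at s = 5%, 0.033 at s = 20%, 0.021 at s = 50%. This shows sensitivity and is not an estimate of the bias.

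**The case against.** The strongest reply is that the codes are openly a draft. Section 9.7 defers to an a priori SAP, the column header says the list is not final, and the placing of single MedDRA terms is ordinary SAP work. This stands for the individual terms: taken alone, they are items to check when the list is finalised. It does not dispose of the main point. The Protocol does not leave the CV endpoint open; it states it twice, differently, and an SAP that follows one section contradicts the other.

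Several stronger readings are tempting and are not supported:

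- A reader might infer that any vaguely coded stroke is lost. It is not. The generic term Cerebrovascular accident counts when non-fatal, as do Haemorrhagic stroke and Cerebral ischaemia. The loss is confined to particular terms.
- A reader might put a percentage on the undercount. Any such figure would need the stroke share, the non-fatal fraction and the use of each term, and would have to allow for the other fatal CV events in the rate. None of these is given.
- A reader might infer an undercount whichever section is followed. It exists only under Table 2, and relative to the MACE wording, which stands in the ARTIS column of that row. Section 9.3.2 does not name stroke.
- A reader might infer that harmonisation with other registers has failed. The promise is in the future tense, the MedDRA column is already shared by three registers, and no comparison with other cohorts is planned, so a difference from ARTIS does not itself bias this study's rate.
- A reader might infer that the list will be selected after the events are seen. The header's wording permits that reading, but it is ambiguous, it covers every row of the table, and the a priori SAP limits it.

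**Conclusion.** The contradiction is real and can be read directly from the text. Section 9.3.2 and the CV risk row of Table 2 define different, non-nested endpoints, and the draft labels do not reconcile them. Following Table 2 also leaves out non-fatal events under four named stroke terms and related bleeding terms, while close equivalents count. That is an undercount relative to the row's own MACE wording. Its size cannot be computed from the Protocol and depends on how often those terms are used for survivors. Table 1 is arithmetically correct and is not affected. The study is descriptive, so no test or error rate is at stake. What is at stake is the meaning of the rate for one of its four safety topics, and this should be settled before any event data are extracted.

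**What to change.** 1. Use the same definition or definitions in Section 9.3.2 and Table 2. One workable form is two named endpoints: (a) MACE, meaning MI, stroke and CV death; and (b) cardiac disorders, including non-fatal heart failure.
2. For MACE, move the cerebral infarction, cerebral thrombosis and intracranial and subarachnoid haemorrhage terms to the block counted whether or not fatal.
3. Review whether Carotid angioplasty, a procedure term, belongs in the list.
4. Replace the header's open wording with a statement that the list is frozen in the a priori SAP before event extraction. Section 9.7 places crude event rates in the 12-monthly analyses, so the freeze should precede the first of these that uses event data.

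The cost is Protocol and SAP wording and a code-list edit. The downside is that two CV rates are reported instead of one. No new data are needed.
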